2.1.5 Other endpoints

The proportion of patients with LDL-C <25 mg/dL (<0.65 mmol/L) within the treatment period of the parallel and single-arm periods (and with two consecutive results below this limit if applicable, spaced out by at least 21 days) and the time to the first LDL-C <25 mg/dL for these patients will be provided. The same analysis will be provided with 15 mg/dL (0.39 mmol/L).

2.2 DISPOSITION OF PATIENTS

This section describes patient disposition for both patient study status and the patient analysis populations.

Screened patients are defined as any patient who met the inclusion criteria and signed the informed consent.

Randomized patients consist of all screened patients with a treatment kit number allocated and recorded in the Interactive Response Technology database, regardless of whether the treatment kit was used. Patients treated without being randomized or treated with a double-blind treatment kit before the randomization will not be considered as randomized and will not be included in any analysis population. For patient study status, the following analyses will be performed in each period separately (by treatment group for parallel-arm period and overall for the single-arm period), if applicable:

- Screened patients
- Screen failure patients and reasons for screen failure
- Nonrandomized but treated patients (if any)
- Randomized patients
- Patients who completed the study treatment period as per protocol
- Patients who prematurely discontinued study treatment by main reason for permanent treatment discontinuation
- Status at last study contact (Alive/ Dead)

All critical or major deviations potentially impacting analyses, randomization, and drug-dispensing irregularities, and other major or critical deviations will be summarized in tables giving numbers and percentages of deviations by treatment group (when applicable).

Additionally, the following populations (for each study periods) will be summarized by treatment group for the populations of the parallel-arm period and overall for the populations of the single-arm period.

- Randomized population
- mITT population
- Safety population
- PKs population
- ADA population

Definitions of the study populations are provided in [Section 2.3](#).

2.2.1 Randomization and drug dispensing irregularities

Randomization and drug-dispensing irregularities occur whenever:

1. A randomization is not in accordance with the protocol-defined randomization method, such as a patient is randomized twice.
OR
2. A patient is dispensed an IMP kit not allocated by the protocol-defined randomization (which may or may not contain the correct-as-randomized IMP), or b) a nonrandomized patient is treated with IMP reserved for randomized patients.

Randomization and drug-dispensing irregularities will be monitored throughout the study and reviewed on an ongoing basis.

Randomization and drug-dispensing irregularities to be prospectively identified include but are not limited to:

Randomization and drug allocation irregularities
Kit dispensation without Interactive Response Technology transaction
Erroneous kit dispensation
Patient randomized twice

2.3 ANALYSIS POPULATIONS

Patients treated without or before being randomized will not be considered randomized and will not be included in any analysis populations. The safety experience of patients treated and not randomized will be reported separately.

Randomized population: includes all randomized patients as defined in [Section 2.2](#).

For any patient randomized more than once, only the data associated with the first randomization will be used in any analysis population. The safety experience associated with any later randomization will be assessed separately.

2.3.1 Modified intent-to-treat population

The mITT population of the parallel arms period will consist of all randomized patients who received at least 1 dose or part of a dose of IMP during this period and who had an evaluable value of LDL-C at baseline and an on-treatment LDL-C value within Week 4 analysis window. Patients in this mITT population will be analyzed according to the auto-injector device group allocated by randomization (ie, as-randomized treatment group).

The mITT population of the single arm period will consist of all randomized patients who continued in single arm period and received at least 1 dose or part of a dose of IMP during this period and who had an evaluable value of LDL-C at baseline and at least one on-treatment LDL-C within one of the analysis windows from Week 8 to Week 16.

The treatment periods are defined in [Section 2.1.4.5](#).

2.3.2 Safety population

The safety population of the parallel arms period will consist of all randomized patients who received at least 1 dose or part of a dose of IMP during this period. Patient data will be analyzed according to the auto-injector device actually used.

The safety population of the single-arm period will consist of all randomized patients who continued in the single-arm period and receive at least 1 dose or part of a dose of IMP during this period.

All safety and PTC analyses will be performed on these populations.

In addition:

- Nonrandomized but treated patients (if any) will not be part of the safety population, but their safety data will be presented separately.
- Randomized patients for whom it is unclear whether they took the IMP will be included in the safety population as randomized.

2.3.3 Pharmacokinetic populations

The PK population of the parallel arms period will consist of all randomized patients who received at least 1 dose or part of a dose of IMP (safety population) and had at least one evaluable blood sample for PK during this period. All patients will be analyzed according to the auto-injector device that they actually received.

The PK population of the single arm period will consist of all randomized patients who received at least 1 dose or part of a dose of IMP and had at least one evaluable blood sample for PK during this period.

The PK population will be used for the analyses of alirocumab concentrations and PCSK9 concentrations.

2.3.4 Anti-alirocumab antibody population

The ADA population of the parallel arms period will consist of all randomized patients who received at least 1 dose or part of a dose of IMP during this period (safety population) with an available ADA sample at baseline and at least one post-baseline available ADA sample during this period. All patients will be analyzed according to the auto-injector device that they actually received.

The ADA population of the single arm period will consist of all randomized patients who receive at least 1 dose or part of a dose of IMP during this period (safety population) with an available ADA sample at baseline and at least one post-baseline available ADA sample during this period.

2.4 STATISTICAL METHODS

2.4.1 Demographics and baseline characteristics

Parameters described in [Section 2.1.1](#) will be summarized on the randomized population by treatment group using descriptive statistics.

Continuous data will be summarized using the number of available data, mean, standard deviation (SD), median, minimum, and maximum for each treatment group. Categorical and ordinal data will be summarized using the number and percentage of patients in each treatment group.

Medical and surgical history will be summarized by primary SOC and HLT. The tables will be sorted by internationally agreed order of SOC and by the decreasing frequency of HLT based on the overall incidence across treatment groups. In addition all medical history of specific interest will be presented by treatment group.

2.4.2 Prior or concomitant medications

The prior and concomitant medications will be presented for the safety population.

Medications received during the parallel-arm period will be summarized by treatment group and medications received during the single -arm period will be summarized overall. Medications will be summarized according to the World Health Organization-Drug Dictionary, considering the first digit of the ATC class and the first 3 digits of the ATC class (therapeutic category). All ATC codes corresponding to a medication will be summarized, and patients will be counted once in

each ATC category (anatomic or therapeutic) linked to the medication. Therefore patients may be counted several times for the same medication.

The table for prior medications will be sorted by decreasing frequency of ATC followed by all other therapeutic classes based on the overall incidence across treatment groups. In case of equal frequency across anatomic or therapeutic categories, alphabetical order will be used.

The tables for concomitant medications will be sorted by decreasing frequency of ATC followed by therapeutic class based on the incidence in the SYDNEY group. In case of equal frequency across anatomic or therapeutic categories, alphabetical order will be used.

In addition, concomitant LMTs will be summarized by pre-specified categories, chemical class or therapeutic class and standardized medication name.

2.4.3 Extent of investigational medicinal product exposure and compliance

The extent of IMP exposure and compliance will be assessed and summarized by actual device within the safety population for the parallel-arms period and overall for the single-arm period.

2.4.3.1 Extent of investigational medicinal product exposure

No duration of IMP exposure will be calculated for the parallel-arms period since patients will receive injection(s) at Day 1 only during this period. The proportion of patients having received the first injection(s) will be summarized.

The duration of IMP exposure for the single-arm period is defined as: last IMP injection date - first IMP injection date during this period + 28 days (regardless of unplanned intermittent discontinuations) and will be described quantitatively. The number of injections received during the single-arm period will also be summarized. The number of patients receiving 1, 2 and 3 injections during the single-arm period will be provided.

2.4.3.2 Compliance

No treatment compliance to the IMP will be calculated for the parallel-arms period since patients will receive injection(s) at Day 1 only during this period. For patients randomized to receive the current AI, it will be described whether all patients received the 2 injections as planned.

Treatment compliance to the IMP for the single-arm period will be assessed using the mean injection frequency, defined for each patient, as the average number of days between 2 consecutive injections, that is: $(\text{last injection date} - \text{first injection date during this period}) / (\text{number of injections} - 1)$ for patients receiving at least 2 injections during this period.

2.4.4 Analyses of endpoints

2.4.4.1 Analysis of primary endpoint

The primary endpoint (ie, number [%]) and types of SYDNEY-associated PTCs related to the unsupervised injections will be described on the safety population for the single arm period. The number and % of PTCs will be provided with the 95% CI using Wilson score method. If applicable, the number of PTCs per patient will be described. In addition the type of PTCs will be described.

In addition, all the reported complaints (including complaints not confirmed as fulfilling PTC definition) will be described.

2.4.4.2 Analysis of secondary endpoints

2.4.4.2.1 Device-related endpoints

All secondary device-related endpoints will be analyzed on the safety population using descriptive statistics. In addition, 95% CI for the number of PTCs, number and % of patients with any PTCs will be provided using Wilson score method.

Questionnaires will be analyzed with descriptive statistics.

2.4.4.2.2 Pharmacokinetic variables

All analyses for PK variables will be presented by treatment group for the parallel-arms period and overall for the single-arm period.

All the PK analyses will be performed using the PK population in each period.

PK parameters (C_{max} , t_{max} , AUC_{0-tau} and C_{trough}) will be summarized (mean, geometric mean, median, standard deviation, standard error of mean, coefficient of variation, minimum, and maximum).

For the parallel-arms period, log-transformed C_{max} , AUC_{0-tau} and C_{trough} , estimates and 90% CI for the ratio of geometric means (SYDNEY/ AI) will be provided using an ANCOVA model with treatment group (SYDNEY, AI) as fixed effect and baseline body weight as covariate.

2.4.4.2.3 *Anti-drug antibodies variables*

The following summaries will be performed on the ADA population by treatment group for the parallel-arm period and overall for the single-arm period, taking into account all samples regardless of timing in relation to injections:

- ADA results (negative or positive) by time point
- ADA titers using descriptive statistics (median, minimum, and maximum) for positive ADA by time point
- Number (%) of patients with pre-existing ADA and number (%) of patients with treatment emergent ADA positive response
- Number (%) of patients with persistent/indeterminate /transient treatment-emergent ADA positive response
- Time to onset of treatment-emergent ADA positive response using descriptive statistics.

2.4.4.2.4 *Pharmacodynamic variables (lipid variables)*

Continuous endpoints anticipated to have a normal distribution

Continuous variables anticipated to have a normal distribution (ie, percent change in LDL-C, Total-C, HDL-C at Week 4) will be analyzed in the mITT population of the parallel-arm period using an ANCOVA model with fixed categorical effect of treatment group (SYDNEY, AI), as well as the continuous fixed covariate of corresponding baseline value. LS means and 95% CI will be provided for both SYDNEY and AI.

Depending on the number of missing LDL-C values at Week 4, a sensitivity analysis may be performed using multiple imputations (with baseline LDL-C and device group factors included in the imputation model) using the MI SAS® procedure to impute missing data followed by ANCOVA model. Results will be combined using Rubin's formulae with the SAS MIANALYZE procedure.

Continuous endpoints anticipated to have a non-normal distribution

Continuous variables anticipated to have a non-normal distribution (ie, percent change in TG at Week 4) will be analyzed in the mITT population of the parallel-arm period using the robust regression model with endpoint of interest as response variable using M-estimation (using SAS ROBUSTREG procedure) with treatment group (SYDNEY, AI) and corresponding baseline value as effects to compare treatment effects. Combined means estimates for both treatment groups with their corresponding 95% CIs will be provided.

Descriptive statistics will be provided for the 4 lipid parameters at Week 8, Week 12 and Week 16 on the mITT population of the single-arm period.

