	
180 unsupervised planned injections using SYDNEY. Patients in the AI group will switch to SYDNEY group at the time of the second injection; therefore, it will ensure to have 60 evaluable patients using SYDNEY for the 2nd, 3rd and 4th unsupervised injections.
 
With 60 evaluable patients using SYDNEY, a total of 180 unsupervised injections is expected to be achieved during the study. Expecting a maximum of 3 observed PTC over the 180 injections (observed PTC rate of 1.67%) with SYDNEY, the upper bound of the 2-sided 95% confidence interval (CI) calculated with the Wilson score method will be no higher than 5.2%.
 
Analysis population
 
The primary endpoint will be analyzed on the safety population of the single-arm period that will consist of all randomized patients who continue in the single-arm period (from Week 4, to Week 16), and receive at least 1 dose or part of a dose of Investigational Medicinal Product (IMP) during this period.
 
Analysis of the primary endpoint
 
The primary endpoint (ie, number (%) and type of SYDNEY-associated PTCs at the unsupervised injections) will be described on the safety population for the single-arm period. The number and % of PTCs will be provided with the 95% CI using Wilson score method. If applicable, the number of PTCs per patient will be described.
 
Analysis of secondary endpoints
 
All secondary device-related endpoints will be analyzed on the safety population using descriptive statistics. In addition, 95% CI for the number of PTCs, number and % of patients with any PTCs will be provided using Wilson score method.
 
Pharmacokinetics
 
PK parameters and levels of PCSK9 (total and free) will be summarized descriptively by auto-injector device group.
 
After the first administration only, for log-transformed maximum plasma concentration (C_{max}), area under the curve concentration versus time curve extrapolated to infinity (AUC_{0-tau}) and trough concentration (C_{trough}), the difference between auto-injector devices will be assessed using a linear fixed effects model.
 
Estimate and 90% CI for the ratio of geometric means (SYDNEY/current AI) will be computed for C_{max}, AUC_{0-tau} and C_{trough}.
 
Anti-drug antibodies
 
Results of ADA will be summarized by auto-injector device group using descriptive statistics.
 
Pharmacodynamics
 
Percent and absolute change from baseline in LDL-C will be summarized descriptively for each auto-injector device.
 
At Week 4 only, statistical analyses will compare auto-injector devices using an ANCOVA model to determine the estimates and 95% confidence intervals for the difference between means of percent LDL-C change for AI versus SYDNEY.

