5.2 SECONDARY

Device-related:

- To collect real-use (usability) data assessing the robustness and user interaction of SYDNEY and the current 1 mL alirocumab auto-injector device (which is referred to as AI) in supervised settings on Week 0 (Day 1).

Pharmacokinetics:

- To compare alirocumab PK 300 mg Q4W administered using SYDNEY and AI, from baseline until Week 4.
- To evaluate alirocumab PK 300 mg Q4W administered using SYDNEY, until Week 16.

Anti-drug antibodies:

- To evaluate the development of anti-drug (alirocumab) antibodies (ADA).

Efficacy/pharmacodynamics:

- To compare the percent and absolute change in LDL-C, from baseline to Week 4 using SYDNEY and AI.
- To evaluate the percent and absolute change in LDL-C from baseline to Weeks 8, 12 and 16, using SYDNEY.

Safety:

- To evaluate the safety and tolerability of alirocumab 300 mg Q4W, using both SYDNEY and AI.

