11.4.6 Analyses of efficacy variables

Lipid variables will be summarized (mean, median, standard deviation, minimum, and maximum) in percent and absolute change from baseline (See efficacy assessments - [Section 9.2.4](#)).

In addition, at Week 4 only, percent change from baseline in LDL-C will be analyzed using an ANCOVA model to determine the estimates and 95% confidence intervals for both SYDNEY and AI.

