1.2.2 Secondary objectives

Device related:

- To collect real-use (usability) data assessing the robustness and user interaction of SYDNEY and the current AI 1 mL alirocumab auto-injector device in supervised settings on Week 0 (Day 1).

Pharmacokinetics:

- To compare alirocumab pharmacokinetics 300 mg Q4W administered using SYDNEY and the current AI, from baseline until Week 4.
- To evaluate alirocumab PK 300 mg Q4W administered using SYDNEY, until Week 16.

Anti-drug antibodies:

- To evaluate the development of ADA.

Pharmacodynamics:

- To compare the percent and absolute change in LDL-C from baseline to Week 4 using SYDNEY and the current AI.
- To evaluate the percent and absolute change in LDL-C from baseline to Weeks 8, 12 and 16, using SYDNEY.

Safety:

- To evaluate the safety and tolerability of alirocumab 300 mg Q4W, using both Auto Injector Devices.

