1.5 MODIFICATIONS TO THE STATISTICAL SECTION OF THE PROTOCOL

Not applicable.

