1.6 STATISTICAL MODIFICATIONS MADE IN THE STATISTICAL ANALYSIS PLAN

Not applicable.

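### Week 4 LDL-C: the promised device difference is not among the listed outputs, and two linked rules (on-treatment cut-off, imputation population) do not work as written

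*SAP*

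**What the plan says.** **Objective.** Protocol 5.2: "To compare the percent and absolute change in LDL-C, from baseline to Week 4 using SYDNEY and AI". SAP 1.2.2 repeats it: "To compare the percent and absolute change in LDL-C from baseline to Week 4 using SYDNEY and the current AI".

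**Planned Week 4 output for percent change in LDL-C.**
- Protocol synopsis, pharmacodynamics: an ANCOVA comparing the devices will give "the estimates and 95% confidence intervals for the difference between means of percent LDL-C change for AI versus SYDNEY".
- Protocol 11.4.6: an ANCOVA will give "estimates and 95% confidence intervals for both SYDNEY and AI".
- SAP 2.4.4.2.4: an ANCOVA with device group and baseline value, also used for Total-C and HDL-C, after which "LS means and 95% CI will be provided for both SYDNEY and AI".
- SAP 2.4.4.2.4, triglycerides: a robust regression, after which "Combined means estimates for both treatment groups with their corresponding 95% CIs will be provided".

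For PK, by contrast, SAP 2.4.4.2.2 names the between-device result: the SYDNEY/AI ratio of geometric means with a 90% CI.

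**Which Week 4 values count.** SAP 2.3.1 admits a patient to the parallel-arm mITT only with a baseline LDL-C and an on-treatment LDL-C in the Week 4 window (Days 15 to 42, SAP 2.5.4). SAP 2.1.4.5 ends the parallel-arm treatment period on the day before the second injection or 35 days after the first, whichever is earlier; protocol 11.3.1 and 11.4.4 say the same. In the protocol flow chart (1.2), Week 4 lipids fall at the visit of the second injection, and footnote o requires them to be drawn before dosing.

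**Missing values.** SAP 2.4.4.2.4 allows a multiple-imputation sensitivity analysis, depending on how many Week 4 LDL-C values are missing. It gives no population for it other than the mITT named for the main analysis.

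**Absolute change.** Protocol 9.2.4 makes absolute LDL-C change an endpoint at Weeks 4, 8, 12 and 16, and protocol 11.4.5 and 11.4.6 call for its summary. SAP 2.1.4.4 names percent change only, and the descriptive lipid statistics listed in SAP 2.4.4.2.4 are for Weeks 8, 12 and 16.

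**The concern.** An objective to compare two devices is answered by an estimate of the difference and its uncertainty. Two separate means with their own intervals leave the reader to do the subtraction, and comparing the intervals by eye gives a poor sense of the precision of the difference. If the contrast is not listed, its direction and form will be chosen after the data are seen.

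The on-treatment cut-off could do more damage. Applied literally by a programmer, it would remove the scheduled Week 4 sample of nearly every patient who follows the protocol, and with it the patient from the mITT. The imputation that is meant to deal with missing Week 4 values could not help, because its population excludes anyone with a missing value.

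**Working it through.** **1. The outputs side by side**

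| Source | Difference between devices listed? |
|---|---|
| Objectives (protocol 5.2, SAP 1.2.2) | comparison required |
| Protocol synopsis | yes, with 95% CI |
| Protocol 11.4.6 | no, each device only |
| SAP 2.4.4.2.4 (LDL-C) | no, each device only |
| SAP 2.4.4.2.2 (PK) | yes, ratio with 90% CI |

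The conflict is mainly between the synopsis and the protocol body; the SAP follows the body.

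**2. What the missing interval would look like**

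The plan gives no precision figure for LDL-C, so there is none to reproduce. Inputs: n = 30 evaluable per arm (protocol 11.1); residual SD of percent change not given, so assumed over 15 to 30 points; one covariate, so df = 2 × 30 − 3 = 57 and t = 2.0025.

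- Half-width per device: t × SD / √n
- Half-width of the difference: t × SD × √(2/n)

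| Assumed SD | Per device | Difference |
|---|---|---|
| 15 | 5.48 | 7.76 |
| 20 | 7.31 | 10.34 |
| 25 | 9.14 | 12.93 |
| 30 | 10.97 | 15.51 |

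The ratio is √2 = 1.41 throughout. At SD 20, the two per-device intervals separate only when the means differ by more than 2 × 7.31 = 14.62 points, whereas the interval for the difference excludes zero beyond 10.34. Overlap is therefore a misleading guide.

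**3. Can the reader rebuild it?**

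Nearly. Let d be the baseline imbalance in SD units and s the residual SD.

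- Variance of the difference: s²[2/n + d²/(2n − 2)]
- Sum of the two per-device variances: s²[2/n + d²/(2(2n − 2))]

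With n = 30 and d = 0.25: 0.06667 + 0.00108 = 0.06774 against 0.06667 + 0.00054 = 0.06721. The square root of the ratio is 0.996, so the SE is understated by 0.4%. With d = 0.5: 0.07098 against 0.06882, understated by 1.5%.

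**4. The on-treatment cut-off**

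- First injection on Day 1; lipid sample and then second injection at the Day 29 visit.
- Treatment period: the earlier of Day 28 (the day before the second injection) and Day 36 (Day 1 + 35), so it ends on Day 28.
- The Day 29 pre-dose sample is therefore off treatment.
- The flow chart schedules no other lipid sample between Day 1 and Week 4; Weeks 1 to 3 are PK visits. Without an unscheduled lipid sample on Days 15 to 28, the patient has no on-treatment Week 4 LDL-C and leaves the mITT.
- The value is not picked up later: the single-arm mITT looks only at the Week 8 to Week 16 windows.

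The same holds anywhere in the ±3-day visit window when sample and injection share a day. The exceptions are patients sampled on an earlier day and patients who never take the second injection and are sampled by Day 36.

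**5. The imputation**

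The mITT requires a Week 4 value, so the number of missing Week 4 values inside it is 0 by definition. The two rules also interact: if the population is widened but the cut-off stays literal, most Week 4 values become missing and would have to be imputed from very few observed ones. The cut-off has to be settled first.

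**The case against.** The best defence is that nothing is lost. Device group is in the ANCOVA, so the contrast comes with the fit; the SAP sentence does not rule it out; the synopsis commitment still stands; and step 3 shows how closely the result can be rebuilt. Protocol 4.2.2 calls the Week 4 comparison descriptive, and no margin or test depends on it. All of that stands and limits the weight of the point. It does not remove the point: the same SAP states the contrast explicitly for PK, so a table programmer has no reason to assume one for LDL-C.

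Some stronger readings are tempting but not supported:

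- **An undeclared departure in the SAP.** The SAP sections headed "MODIFICATIONS TO THE STATISTICAL SECTION OF THE PROTOCOL" and "STATISTICAL MODIFICATIONS MADE IN THE STATISTICAL ANALYSIS PLAN" both say not applicable. On this output that is consistent with protocol 11.4.6, whose wording the SAP follows.
- **A broken promise for all four lipids.** The objective and the synopsis name LDL-C only. The triglyceride model is described as comparing treatments, but no difference is promised for Total-C, HDL-C or triglycerides.
- **A clash between the Day 42 window limit and the 35-day limit.** Days 37 to 42 lie in the window but past Day 36. SAP 2.1.4.4 excludes post-treatment data and SAP 2.3.1 requires an on-treatment value, so this is already handled.
- **A Week 4-only gap in absolute change.** SAP 2.1.4.4 omits absolute change at every visit. General statements in SAP 2 and 2.1.1 about presentation by arm and on-treatment summaries might lead to a Week 4 table, but none is listed.

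On the imputation, it is fair to say that the sentence names no population itself and that the analysis is optional. The mITT is inferred from the preceding paragraph, but it is the only candidate offered.

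**Conclusion.** The point holds as a reporting gap plus two rules that need correcting. The synopsis and objectives call for the Week 4 LDL-C device difference, while protocol 11.4.6 and SAP 2.4.4.2.4 list only per-device estimates. The absent interval would have a half-width of about 7.8 to 15.5 points for an assumed SD of 15 to 30 and 30 patients per arm, 1.41 times that of each per-device interval under equal n and SD. The reader can approximate it to within about 1.5% of its SE for baseline imbalances up to 0.5 SD.

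The cut-off rule has the larger potential effect. Read literally, it excludes most scheduled Week 4 values. How many cannot be stated, because the documents do not say how often sample and injection fall on different days. The sponsor very probably does not intend this, but the text needs to say so.

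The comparison is secondary and descriptive. The primary complaint analysis and the PK analyses are unaffected. The corrections are worth making before database lock.

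**What to change.** In the SAP:

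1. **2.4.4.2.4:** list the LS mean difference between devices, with its 95% CI, for percent change in LDL-C at Week 4. State one direction and use it in both documents. SYDNEY minus AI would match the PK ratio, but the synopsis has AI versus SYDNEY, so one of them must move. Label the result descriptive because no margin is set. Differences for Total-C, HDL-C and triglycerides are optional.
2. **2.1.4.5 or 2.3.1:** state that a lipid sample taken before the second injection on the same day counts as on-treatment for the parallel-arm period.
3. **2.4.4.2.4:** state that the multiple imputation, if run, uses all randomized, treated patients with a baseline LDL-C, analysed as randomized.
4. **2.1.4.4 and 2.4.4.2.4:** add absolute LDL-C change at Weeks 4, 8, 12 and 16, with a Week 4 summary by device.

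At the next protocol amendment, bring 11.4.6 and the synopsis into line on the output and its direction, and add the same-day clarification to 11.3.1 and 11.4.4. A separate amendment is not warranted: protocol 15 requires ethics committee approval for any amendment, and the synopsis already contains the contrast.

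The cost is SAP wording, one contrast from a model already specified and some descriptive output; no patients, samples or visits are added. The one risk is that the interval is over-read as evidence of equivalence, which the descriptive label is there to prevent.
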